5 STUDY SUMMARY

5.1 Study Purpose

The purpose of this study is to demonstrate the efficacy and safety of the Omnipod 5 System compared to pump and CGM therapy in adults with type 1 diabetes currently using pump therapy.

5.2 Study Design

Adults with type 1 diabetes currently on pump therapy with an A1C between 7-11%, inclusive, will be recruited for the study. At least 80% of participants must have an A1C \geq 8%. At least 50% of participants must be using Omnipod for pump therapy at the time

of enrollment.

Following a two-week standard therapy period where CGM data will be collected, participants will be randomized in a 2 (Intervention group):1 (Control group) ratio as follows:

- Intervention Group - Omnipod 5 System with Dexcom G6 CGM or
- Control Group – Participant’s current insulin pump with Dexcom G6 CGM

Both groups will participate in a randomized period for 13-weeks after completion of standard therapy.

A total of up to 200 participants at up to 15 clinical sites in the US and France will be enrolled in the study, to obtain a minimum of 170 randomized participants.

Table 1: Schedule of Assessments

	Screening	Standard Therapy (14-days)	13 Week Follow Up							UV ^f	EW ^e
Visit Number	1 ^a	2 ^a	3	4 ^h	5	6	7	8			
Study Day/Visit Window	Up to 30-days prior to Study Day 1	14-days prior to Study Day 1	1	2 +1d	14 ±3d	30 ±3d	60 ±3d	90 ±3d	N/A		
Telephone (T) or Office (O) Visit	O	O	O	T/O ^d	T/O ^d	T/O ^d	T/O ^d	O	T/O ^d	O	
Screening/Randomization											
Informed Consent	X										
Confirm eligibility	X										
Randomization			X								
Laboratory Assessments											
A1C (Central Lab)	X							X		X	
A1C (Point of Care (POC) for eligibility)	X										
TSH, Serum Creatinine, Lipid Panel ^b	X										
Pregnancy Test (urine dipstick) ^l	X		X								
Clinical Assessments											
Medical History	X										
Demographics	X										
Concomitant medications	X	X	X	X	X	X	X	X		X	
Height	X										
Weight	X							X		X	
Vital signs ^c	X		X	X	X	X	X	X		X	
Electrocardiogram	X										
Adverse events		X	X	X	X	X	X	X	X	X	
Insulin Delivery (Control arm only after visit 3) ^k			X			X	X	X		X	

Questionnaires (See Table 2)										
Study Devices										
Study device training (BG/ketone meter, and CGM)		X								
Dispense/Return QC Tested BG/ketone meter, and CGM		X ^h						X ⁱ		X ⁱ
Study CGM sensor placement (Enrollment)		X								
Start/Stop CGM data collection		X						X		X
Assess CGM usage to ensure data criteria has been met ^g		X ^g	X							
Training on Glucagon administration and information on treatment of hypo/hyperglycemia		X								
Omnipod 5 training (Intervention arm only)			X							
Dispense/Return Omnipod 5 System (Intervention arm only)			X					X		X
Data Portal initiation/discontinuation (Intervention arm only)			X					X		X
Complaints/device deficiencies			X	X	X	X	X	X	X	X
BG/ketone meter data review ^d				X	X	X	X	X		X
Pump and CGM data review				X	X	X	X	X	X	X

^aScreening and Standard Therapy visits may be completed on the same day

^bTSH, Serum Creatinine and Lipid Panel (includes total cholesterol, HDL, LDL, triglycerides) laboratory assessments within the past 60 days may be used for screening

^cVital signs include body temperature, respirations, pulse, and blood pressure should be performed at all in person visits

^dVisits identified as "T/O" can either be conducted in person at the clinical site or over the telephone. Visits identified as "O" can only be conducted in person at the clinical site. Vital signs are not required at any visit conducted via telephone, however, BG/Ketone meter data review should still occur

^eEarly withdrawal visit will only be conducted for participants who complete visit 3 and discontinue prior to visit 8

^fUnscheduled visits will serve as extra study visits, if needed

^gParticipants meeting the CGM usage and data criteria with their own Dexcom G6 will be eligible to immediately commence the study at Visit 3 (in which case, visit 1, visit 2, and visit 3 may occur on the same day). CGM data for EU subjects during Standard Therapy will be collected prospectively, and thus EU Subjects will need to participate in the full 14-day Standard Therapy phase.

^hBG/ketone meter must pass at least one level of quality control testing prior to dispensing

ⁱUndispensed BG/ketone meters do not need to be returned to sponsor

^jPregnancy tests are only required at both visit 1 and visit 3 if these visits do not occur on the same day

^kInsulin delivery data will be collected and documented on a case report form for the control arm, the intervention arm data will automatically be collected by Insulet cloud

Abbreviations: S=Screening; EW=Early Withdrawal; QC=Quality Control Testing; UV=Unscheduled Visit

Table 2: Patient Reported Outcomes (Questionnaires)

Visit	Adult (ages 18-70)
Visit 2 Standard Therapy	Clarke EQ-5D-3L T1DDS DQOL-brief DIDP HCS PSQI SUS INSPIRE-Adult
Visit 8 (End of Study) or Early Withdrawal	Clarke EQ-5D-3L T1DDS DQOL-brief DIDP HCS PSQI SUS INSPIRE-Adult

6 OBJECTIVES AND ENDPOINTS

6.1 Primary Objective

To demonstrate superior efficacy of the Omnipod 5 System compared to pump and CGM therapy in adults with type 1 diabetes.

6.1.1 Primary Endpoint

The primary endpoint is per-participant percentage of time in range (TIR) 70-180 mg/dL as measured by study CGM and comparing the Intervention group to the Control group during the 13 week randomized period.

6.2 Secondary Objective

To demonstrate additional measures of efficacy and safety of the Omnipod 5 System compared to pump and CGM therapy in adults with type 1 diabetes.

6.2.1 Secondary Endpoints

The following secondary per-participant endpoints will be evaluated and compared in the Intervention group vs. Control group at the end of the 13-week randomized period:

- Percentage of time <54 mg/dL (non-inferiority)
- Percentage of time >180 mg/dL
- Mean glucose
- Change from baseline in A1C
- Percentage of time < 70 mg/dL
- Change from baseline in T1-DDS total score
- Change from baseline in HCS total score
- Change from baseline in DQOL-brief total score

6.3 Exploratory Endpoints

The following exploratory endpoints will be evaluated and compared in the Intervention group vs. Control group at the end of the 13-week randomized period:

- Proportion of participants with A1C <7%
- Proportion of participants with A1C <8%
- Proportion of participants with ≥1% improvement in A1C from baseline
- Proportion of participants with ≥10 relative percentage point improvement in A1C from baseline
- Proportion of participants with either ≥1% improvement in A1C from baseline OR ≥10 relative percentage point improvement in A1C from baseline
- Change from baseline in Body Mass Index (BMI)
- Change from baseline in total daily insulin (TDI) (units/kg)
- Additional CGM-derived endpoints, such as coefficient of variation, time above range >250 mg/dL, percentage of time < 54 mg/dL (superiority), TIR during daytime and nighttime hours
- Number of episodes of severe hypoglycemia
- Number of episodes of DKA

6.4 Patient Reported Outcomes

Questionnaires will be used to evaluate general and disease-specific quality of life, and device usability. Results will be assessed at 13 weeks compared to baseline (Intervention and Control group)

- Clarke Hypoglycemia Awareness
- EQ-5D-3L – Used to measure quality of life
- T1-DDS¹ – Used to measure four critical dimensions of distress
- DQOL-brief² – Used to assess the relative burden of an intensive diabetes treatment regimen
- DIDP – Used to assess the perceived impact of diabetes in physical health, finances, relationships with family/friends, leisure activities, work/studies and emotional well-being
- HCS³ – Used to measure hypoglycemia unawareness, hypoglycemia frequency, severity, and impact
- PSQI – Used to measure sleep disturbance and usual sleep habits
- SUS – Used to measure usability of a system
- INSPIRE – Used to evaluate the impact of AID systems on the psychosocial functioning and quality of life

7 SCREENING AND ELIGIBILITY

A total of up to 200 participants aged 18-70 years with type 1 diabetes currently on pump therapy with an A1C between 7-11%, inclusive, will be recruited for the study. A screening visit will be scheduled for the potential participant for the clinical site to assess eligibility. Participants who appear to meet the eligibility criteria will review and sign an informed consent form (ICF). Once the informed consent form has been signed and eligibility assessments have been completed and confirmed, study participants will be eligible to enroll in the study. Enrollment will occur when the participant begins wearing the Dexcom G6 CGM dispensed for the study. All study participants will receive Dexcom G6 CGM device training prior to enrollment. Commencement of the standard therapy period will follow placement of the Dexcom G6 CGM.

Participants who do not meet the eligibility criteria will not continue in the study and will be considered screen failures.

Laboratory results within the last 60 days, except for A1C, may also be used if available.

At the conclusion of the standard therapy period, participants will be randomized and assigned to either the Intervention group or the Control group using 2:1 randomization. Twice as many participants are expected to be randomized to the Intervention group versus the Control group.

After completing the 14-day standard therapy period, participants randomized to the Intervention arm will be trained on the Omnipod 5 system, and all participants will transition to the 13-week period of the study. Participants randomized to the control arm

¹ Change from baseline in T1-DDS total score at 13 weeks is a secondary endpoint.

² Change from baseline in DQOL-brief total score at 13 weeks

³ Change from baseline in HCS total score at 13 weeks is a secondary endpoint.

will continue their usual pump therapy for the 13-week period of the study while using the study CGM.

7.1 Visit 1 (Up to 30 days prior to Study Day 1)

Visit 1 will be conducted in person at the clinical study site. This visit will assess eligibility and will include:

- Signing of informed consent
- Review of inclusion/exclusion criteria and confirmation of eligibility
- Assessments performed following Table 1: Schedule of Assessments

7.1.1 Informed Consent

Participants who appear to meet the eligibility criteria will be asked to review and sign an ICF approved by each respective Institutional Review Board (IRB) or Ethics Committee (EC) for participation in the study before any procedure or collection of any data that are not part of usual care.

Participants will be required to sign a statement of informed consent that meets the requirements of 21 CFR part 50, local regulations, ICH guidelines, Health Insurance Portability and Accountability Act (HIPAA) requirements, where applicable, and the IRB/IEC or study center.

After informed consent is obtained, a participant identification number will be issued to uniquely identify each participant. The unique identifier will be used to identify the participant throughout the study and will be used for all source documents and electronic Case Report Forms (eCRFs).

7.1.2 Confirm Eligibility

7.1.2.1 Inclusion Criteria

Participants must meet all the following criteria to be enrolled in the study:

1. Age at time of consent 18-70 years of age
2. Diagnosed with type 1 diabetes for at least 1 year. Diagnosis is based on investigator's clinical judgment.
3. On pump therapy for at least ≥ 3 months prior to screening and familiar with pump therapy concepts such as basal and bolus insulin delivery, and carbohydrate counting. Participants using automated insulin delivery (AID) devices, including devices with predictive low glucose suspend (PLGS), in the 3 months prior to screening, will be excluded from participating.
4. A1C 7.0-11.0% by point-of-care taken at screening visit
5. Willing to use and obtain U-100 insulin: (either insulin aspart (Novolog, NovoRapid), or insulin lispro (Humalog, Admelog)), as the primary insulin treatment
6. Must have a smartphone that supports the Dexcom app download and participants must be willing to use the app throughout the study
7. Investigator has confidence that the participant can safely operate all study devices and can adhere to the protocol
8. Willing to wear the system continuously throughout the study
9. Willing and able to sign the Informed Consent Form (ICF)

7.1.2.2 Exclusion Criteria

Participants who meet any of the following criteria will be excluded from the study:

1. Any medical condition, such as untreated malignancy, unstable cardiac disease, unstable or end-stage renal failure, eating disorders, or other conditions which in the opinion of the investigator, would put the participant at an unacceptable safety risk
2. History of severe hypoglycemia in the past 6 months
3. History of diabetic ketoacidosis (DKA) in the past 6 months, unrelated to an intercurrent illness or infusion set failure
4. Blood disorder or dyscrasia within 3 months prior to screening, including use of hydroxyurea, which in the investigator's opinion could interfere with determination of HbA1C
5. Currently on systemic steroids or intends to receive systemic steroid treatment in the next 6 months, including stable treatment for adrenal insufficiency. Inhaled, ophthalmic, topical, joint injection, and other locally applied steroids are allowed.
6. Unable to tolerate adhesive tape or has any unresolved skin condition in the area of sensor or pump placement
7. Use of non-insulin anti-hyperglycemic medication other than metformin, in the 12 weeks prior to the Baseline Visit. Participants taking metformin should remain on a steady dose during study participation.
8. Pregnant or lactating, or is a woman of childbearing potential and not on acceptable form of birth control (acceptable forms of contraception include abstinence, barrier methods such as condoms, hormonal contraceptives, intrauterine device, surgical sterilization such as tubal ligation or hysterectomy, or vasectomized partner)
9. Participation in another clinical study using an investigational drug or device within 30-days or 5 half-lives (whichever is longer) prior to screening, or intends to participate in any other study during this study period
10. Unable to follow clinical protocol for the duration of the study or is otherwise deemed unacceptable to participate in the study per the investigator's clinical judgment
11. Participant is an employee of Insulet, an Investigator or Investigator's study team, or immediate family member of any of the aforementioned

7.1.3 Lab and Clinical Screening Assessments

Participants who have signed the informed consent and appear to meet the eligibility criteria will continue to the screening assessments which will be performed at the clinical study site.

Assessments may be completed up to 30-days prior to enrollment. Participants are considered enrolled upon placement of the first study CGM. Assessments include the following:

- A1C (Central Lab)
- A1C (Point of Care for eligibility)

- TSH, Serum Creatinine, Lipid Panel (includes total cholesterol, HDL, LDL, triglycerides, assessments within the past 60 days may be used for screening)
- Pregnancy test (urine dipstick) for women of childbearing potential
- Medical history (including prior and current medical conditions and surgical history)
- Demographics (age, gender, race (US only), ethnicity (US only))
- Review of concomitant medications
- Height & weight
- Vital signs (body temperature, respirations, pulse, and blood pressure)
- Electrocardiogram

Clinical sites will send a blood specimen for A1C to a central laboratory. A point of care (POC) A1C will be used to determine eligibility.

7.2 Visit 2 (14-days prior to Study Day 1)

Visit 2 will be conducted in person at the clinical study site and may be combined with Visit 1 if all eligibility criteria are met and laboratory assessments are determined to meet study criteria. All scheduled assessments will be performed according to Table 1: Schedule of Assessments and Table 2: Patient Reported Outcomes (Questionnaires). This visit will include:

- Review of concomitant medications
- Assessment of AEs
- Questionnaires (Table 2: Patient Reported Outcomes (Questionnaires))
- Study device training per manufacturer's instructions (CGM and BG/ketone meter)
- Dispense BG/ketone meter, and CGM:
 - BG/ketone meter
 - Contour[®] Next One blood glucose meter (US sites only)
 - Contour[®] Next One blood glucose meter test strips (US sites only)
 - Precision Xtra blood ketone meter (US sites only)
 - Precision Xtra blood ketone meter test strips (US sites only)
 - FreeStyle Optium Neo blood glucose and ketone meter (EU sites only)
 - FreeStyle Optium Neo blood glucose and ketone strips (EU sites only)
 - Lancets
 - Dexcom G6 CGM (sensor and transmitter)
 - CGM Data Collection Device (EU sites only)
- QC testing of BG/ketone meter
 - Must pass at least one level of quality control testing prior to dispensing
- Study CGM sensor placement (Enrollment)
 - Assess CGM usage and data criteria are met for participants currently using Dexcom G6 (US sites only).
 - Sensor placement location will be reinforced as well as the importance of using approved locations
 - Ensure all participants understand how to troubleshoot sensor errors and avoid over-calibration of sensors
- Start CGM data collection

- Training on glucagon administration and information on treatment of hypo/hyperglycemia

7.2.1 Assessment of CGM Usage and Data Criteria

7.2.1.1 Current Dexcom G6 Users (US Sites Only)

Current Dexcom G6 users may be exempt from the standard therapy 14-day period if the following criteria are met:

- Willing to provide 14-days of CGM data from the past 30-days
- Meet the success criteria of 80% CGM use during any consecutive 14-days in the past 30-days
- Must have $\geq 2,016$ CGM values during the 14-days

The site staff will review the device use and data criteria to see if they have met the exemption criteria. If exemption criteria are not met, participants may choose to continue to collect data until they meet the criteria or will be required to participate in the entire 14-day standard therapy period consistent with the requirements for non-G6 users.

If participants meet the criteria, they will be immediately eligible to proceed with Visit 3, in which case Visit 1, Visit 2, and Visit 3 may occur on the same day, commencing the 13-week study.

7.2.1.2 Non-G6 Users (US Sites Only)

All non-G6 users will be required to participate in the entire standard therapy 14-day period. At the commencement of standard therapy, participants will be dispensed an unblinded Dexcom G6 CGM and will be instructed on how to download the Dexcom app on their personal cellular devices. The site staff will link the participant's Dexcom app with the data collection portal. Participants will commence the 14-day period data collection period.

7.2.1.3 CGM Data Criteria (EU Sites Only)

All subjects in the EU will be required to participate in the entire standard therapy 14-day period. At the commencement of standard therapy, participants will be dispensed a Dexcom G6 CGM and a CGM data collection device. The site staff will link the CGM data collection device with the data portal. Participants will commence the 14-day data collection period.

7.3 CGM Usage

During the standard therapy 14-day period, participants will be asked to do the following:

- Manage their diabetes at home per their usual routine
- Administer meal boluses per their usual dosing routine
- Change their sensor if a sensor fails, or as needed
- Calibrate their CGM, if required, per the manufacturer's instructions
- Monitor their capillary blood glucose (BG) as needed

At the conclusion of the 14-day standard therapy period, the data criteria will be reviewed to see if they have met the device use and data criteria. If criteria are not met, participants may choose to continue to collect data until they meet the criteria. Extending standard therapy past 14-days will not constitute a protocol deviation unless standard therapy extends past 30-days. If participants extend beyond the 14-days, the most recent 14-days of data meeting the criteria defined for CGM use and data criteria will be used in the endpoint analysis.

7.3.1 CGM Initiation

Participants will be provided with the Dexcom G6 CGM and instructed to use the devices throughout the study. Dexcom G6 CGM training will be provided to all participants. Current CGM users will be instructed to remove their personal CGM and place the study Dexcom G6 CGM. Participants will be instructed to only use the study provided Dexcom G6 CGM device for the duration of the study.

Participants will be provided with contact information for the clinical study site and advised to contact the site for any health or device related issues.

7.4 Visit 3 (Study Day 1)

Visit 3 will mark the start of the 13-week study and will commence upon the conclusion of the standard therapy 14-day period and after all assessments are performed according to Table 1: Schedule of Assessments

Visit 3 will be conducted in person at the clinical study site. All scheduled assessments will be performed according to Table 1: Schedule of Assessments This visit will include:

- Randomization
- Pregnancy test (urine dipstick) for women of childbearing potential (required only if Visit 1 and Visit 3 do not occur on the same day)
- Review of concomitant medications
- Vital signs
- Assessment of AEs
- Insulin delivery metrics (e.g., TDI, average basal and bolus insulin dose, and time on device over the past 30 days)
- Assess CGM usage and data criteria has been met (at least 80% CGM use (11.2-days) during any consecutive 14-days in the past 30-days and $\geq 2,016$ CGM values during the 14-days)
- All participants are required to have access to glucagon and receive training on how to deliver the medication
- Omnipod 5 System device training conducted by trained clinical site staff (Intervention arm only)
- Dispense Omnipod 5 System (Intervention group only)
- Data Portal initiation (Intervention group only)
- Dispense Dexcom CGM and confirm data transmission for those in control arm (Control group only)
- Complaints/device deficiencies since last visit

7.4.1 Randomization

Participants who meet all eligibility criteria, have completed all screening assessments, and have met the CGM device usage and data criteria will be randomized 2:1 using a computer-generated randomization scheme stratified by site, A1C (7% to <8% vs. ≥8% to 11%), and Omnipod use (user vs. non-user). A permuted-block randomization scheme will be implemented to balance group assignments. Randomization will be assigned via study database access during Visit 3 to the two study groups (Intervention Group: Omnipod 5 System with Dexcom G6 CGM or Control Group: Participant's current pump with Dexcom G6 CGM).

During the 13-week study period, all participants will be asked to do the following:

- Follow insulin therapy per recommendations from the clinical study staff
- Follow their pre-exercise management such as insulin reduction for meal boluses, consumption of snacks, or adjusting their insulin delivery settings
- Treat themselves per their usual routine if they become hypoglycemic or hyperglycemic or have symptoms of either at any time during the study
- Consume meals and snacks of their own choosing. Participants will be encouraged to estimate the grams of carbohydrates for each meal or snack per their usual routine. The estimate should be entered into the meal bolus calculator.
- Give meal boluses per their usual dosing routine
- Change their CGM per manufacturer's instructions or sooner if necessary
- Change the Pod at least once every 72 hours (Intervention group only)
- Change pump infusion site as recommended by manufacturer

In the event of unexplained hyperglycemia, where the CGM is >300mg/dL for 1 hour or >250 mg/dL for 2 hours, blood glucose (measured with BG meter) and ketones should be checked. If BG is ≥300 mg/dL and ketones are >1.0 mmol/L, an occlusion or dislodged cannula should be suspected. The Pod or infusion set should be removed, and the participant will be instructed to replace the Pod or infusion set at a different location on the body. Participants should contact the clinical site for further instructions to determine whether an additional injection of insulin is required. This prolonged hyperglycemic event, defined as meter BG ≥300 mg/dL and ketones >1.0 mmol/L, will be recorded as an adverse event.

7.5 Visits 4 and 5

Visit 4 and 5 will be conducted either over the telephone or in person at the clinical study site on study days 2 (+1d) and 14 (±3d) respectively. All scheduled assessments will be performed according to Table 1: Schedule of Assessments. These visits will include:

- Review of concomitant medications
- Vital signs (for in person visits)
- Assessment of AEs
- Complaints/device deficiencies since last visit
- BG/ketone meter data review by clinician

- Pump and CGM data review by clinician

7.6 Visits 6 and 7

Visit 6 and 7 will be conducted either over the telephone or in person at the clinical study site on study day 30 ($\pm 3d$) and 60 ($\pm 3d$). All scheduled assessments will be performed according to Table 1: Schedule of Assessments This visit will include:

- Review of concomitant medications
- Vital signs (for in person visits)
- Assessment of AEs
- Complaints/device deficiencies since last visit
- BG/ketone meter data review by clinician
- Insulin delivery metrics (e.g., TDI, average basal and bolus insulin dose, and time on device over the past 30 days) (Control group only)
- Pump and CGM data review by clinician

7.7 Visit 8

Visit 8 will be conducted in person at the clinical study site on study day 90($\pm 3d$). All scheduled assessments will be performed according to Table 1: Schedule of Assessments This visit will include:

- A1C (central laboratory)
- Review of concomitant medications
- Weight
- Vital signs
- Assessment of AEs
- Insulin delivery metrics (e.g., TDI, average basal and bolus insulin dose, and time on device over the past 30 days) (Control group only)
- Completion of questionnaires (Table 2: Patient Reported Outcomes (Questionnaires))
- Return BG meter, Ketone meter, and study CGM, if unused
- Stop CGM data collection
- Return Omnipod 5 System (Intervention group only)
- Data Portal (Intervention group only) discontinuation
- Complaints/device deficiencies since last visit
- BG/ketone meter data review by clinician
- Pump and CGM Data review by clinician

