9.2 Hypoglycemia/Hyperglycemia

Participants will be asked to treat per their usual routine if they suspect either hypoglycemia or hyperglycemia, either by confirmation of hypoglycemia with a fingerstick BG, symptoms, or perceived risk.

Participants will be encouraged to manage their hyperglycemia per their usual routine. This includes checking for ketones and administering a correction bolus if needed.

In the event of unexplained hyperglycemia, where the CGM is $>300\text{mg/dL}$ for 1 hour or $>250\text{ mg/dL}$ for 2 hours, blood glucose (measured with BG meter) and ketones should be checked. If BG is $\geq 300\text{ mg/dL}$ and ketones are $>1.0\text{ mmol/L}$, an occlusion or dislodged cannula should be suspected. The Pod or infusion set should be removed, and the participant will be instructed to replace the Pod or infusion set at a different location on the body. Participants should contact the clinical site for further instructions to determine whether an additional injection of insulin is required. This prolonged hyperglycemic event, defined as meter BG $\geq 300\text{ mg/dL}$ and ketones $>1.0\text{ mmol/L}$, will be recorded as an adverse event.

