9.6 Hyperglycemic/Ketotic Events

Hyperglycemia is only reportable as an adverse event when any of the following criteria is met:

- The event involved DKA, as defined by the Diabetes Control and Complications Trial (DCCT)²⁰, i.e. if all of the following are present:
 - Symptoms such as polyuria, polydipsia, nausea, or vomiting;
 - Serum ketones >1.5 mmol/L or large/moderate urine ketones;
 - Either arterial blood pH <7.30 or venous pH <7.24 or serum bicarbonate <15; and
 - Treatment provided in a health care facility
- Evaluation or treatment was obtained at a health care provider facility for an acute event involving hyperglycemia or ketosis, or the participant contacted the site and received guidance on how to manage the hyperglycemia/ketosis
- Prolonged hyperglycemia: defined as meter BG \geq 300 mg/dL for over 1 hour and ketones >1.0 mmol/L
- Hyperglycemia resulting in an SAE that may not otherwise meet the above criteria

When a hyperglycemia/ketotic event meets the above reporting requirements, Adverse Event Form should be completed.

Events meeting DKA criteria should be considered a serious adverse event and follow the SAE reporting requirements. Hyperglycemia events not meeting criteria for DKA generally will not be considered as serious adverse events unless one of the SAE criteria above is met

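### For unexplained, CGM-triggered hyperglycemia managed without site guidance or care, Protocol 7.4.1 and 9.2 record an adverse event that 9.6 makes reportable only if meter BG stays ≥300 mg/dL for over 1 hour

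*Protocol*

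**What the plan says.** Protocol 7.4.1 covers unexplained hyperglycemia "where the CGM is >300mg/dL for 1 hour or >250 mg/dL for 2 hours". Meter BG and ketones are then checked. On a positive check the participant replaces the Pod or infusion set, and: "Participants should contact the clinical site for further instructions to determine whether an additional injection of insulin is required". The paragraph ends: "This prolonged hyperglycemic event, defined as meter BG ≥300 mg/dL and ketones >1.0 mmol/L, will be recorded as an adverse event". Protocol 9.2, in the safety chapter, repeats the rule ("This prolonged hyperglycemic event, defined as meter BG" and the same thresholds).

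Protocol 9.6 opens with a restriction: "Hyperglycemia is only reportable as an adverse event when any of the following criteria is met". Its prolonged-hyperglycemia item has the same two thresholds but adds a time, with meter BG at or above "300 mg/dL for over 1 hour and ketones >1.0 mmol/L". The other items are DKA, an SAE, evaluation or treatment at a health care facility, and the case where "the participant contacted the site and received guidance on how to manage the hyperglycemia/ketosis". It then ties the paperwork to that list: "When a hyperglycemia/ketotic event meets the above reporting requirements, Adverse Event Form should be completed".

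Protocol 9.4 makes hyperglycemic/ketotic events reportable as defined (item 7) and drops any adverse device effect that 9.6 excludes (item 2). The SAP prevails over the protocol (SAP 1, Protocol 12.7) but does not define prolonged hyperglycemia. SAP 6.5 tabulates whatever adverse events are reported.

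**The concern.** One named event has two definitions, and both are binding. Sections 7.4.1 and 9.2 say that the event is recorded. Section 9.6 says that hyperglycemia is not reportable unless an item on its list is met. For an event that meets the first rule and nothing on the list, a site cannot follow both.

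Such an event can come to light. Clinicians review BG/ketone meter data and pump and CGM data at Visits 4 to 8 (Protocol 7.5 to 7.7), so a site may find an event that the participant dealt with alone. One site could complete the form under 7.4.1 and 9.2, and another could leave it out under 9.6. The same clinical event would then be counted differently in the adverse event tables of a trial whose secondary objective includes safety.

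**Working it through.** The check is a comparison of rules. The plan gives no figure to reproduce.

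**Rule A (Protocol 7.4.1, 9.2).** Unexplained hyperglycemia, and CGM >300 mg/dL for 1 hour or >250 mg/dL for 2 hours, and meter BG ≥300 mg/dL, and ketones >1.0 mmol/L. Meter time required: none.

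**Rule B (Protocol 9.6).** Meter BG ≥300 mg/dL for more than 60 minutes and ketones >1.0 mmol/L; or DKA; or facility care; or site guidance; or an SAE.

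**Does the CGM trigger supply the hour in 9.6?** No. It is CGM time, whereas 9.6 specifies meter BG. The 2-hour branch can also be met with every CGM value below 300 mg/dL.

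**Illustrative event.** CGM at 285 mg/dL for 120 minutes, unexplained; one check with meter BG 305 mg/dL and ketones 1.2 mmol/L; Pod changed; site not called; found at the day 30 review. These values are invented to test the rules.

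- Trigger: 285 > 300 is false; 285 > 250 for 120 minutes is true. Met.
- Rule A: 305 ≥ 300 and 1.2 > 1.0. Record.
- Rule B: a single reading does not show more than 60 minutes at ≥300 mg/dL, and no other item applies. Not reportable.
- Protocol 9.4: item 2 gives way to 9.6. The example assumes that items 1 and 3 to 5 are not met (no SAE; no device discontinuation or clinically significant effect on glucose control under item 3; no effect on study procedures; no emergency visit). If a site judged one of them met, the event would be reportable and the conflict would disappear.

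| Event | Rule A | Rule B | Union of A and B |
|---|---|---|---|
| Example above | record | not reportable | reportable |
| Same, participant called and got guidance | record | reportable | reportable |
| Same, second meter BG ≥300 mg/dL more than 60 minutes later | record | reportable | reportable |
| Meter BG ≥300 mg/dL for over 1 hour, ketones >1.0 mmol/L, no CGM trigger | not covered | reportable | reportable |
| One meter BG ≥300 mg/dL, ketones >1.0 mmol/L, cause known, no care or guidance | not covered | not reportable | not reportable |

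Only the first row is a conflict. In the fourth row Rule A is silent and 9.6 governs.

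**The case against.** The strongest reply is that the gap is narrow. Participants in this situation are told to contact the site, and 24-hour contact is provided (Protocol 7.8). Once guidance is given, 9.6 reports the event at any duration and the three sections agree. A reader who looks only at the prolonged-hyperglycemia item might infer that 9.6 shuts out every triggered event lasting an hour or less. The documents do not support that, because the item is one of several alternatives. This part of the objection stands and sets the scope of the point.

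Second, 9.6 does not say how the hour is to be shown. A site could take it to mean hyperglycemia of over an hour confirmed by a meter, and after the >300 mg/dL for 1 hour trigger the two rules would then nearly coincide. That is fair for that branch. It does not help for >250 mg/dL over 2 hours.

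Third, site staff train the Intervention arm on the device (Protocol 7.4) and so know the arm. A reader might infer that reporting would differ by arm. Nothing in the documents shows this: both rules apply to both arms, and knowledge of the arm affects every adverse event in an open-label trial. The adverse event form guidance and the Safety Management Plan are not among the documents either, so actual divergence between sites cannot be shown.

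**Conclusion.** The conflict is real but minor. It is confined to triggered events with meter BG ≥300 mg/dL and ketones >1.0 mmol/L, not shown to last over 1 hour by meter, with no site guidance, facility care, DKA or SAE and no other item of 9.4. These are adverse events under 7.4.1 and 9.2 and not reportable under 9.6, and the SAP does not settle which rule applies.

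The effect is on descriptive adverse event tables and listings. The primary and secondary efficacy endpoints, the severe hypoglycemia and DKA rates that may be tested (SAP 5.2.5) and the participant discontinuation criteria (Protocol 10.1) do not use this definition. The number of such events cannot be estimated from the documents. The conclusion assumes that the time in 9.6 means meter time, as it is written.

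**What to change.** Reword the 9.6 item as the union of the two existing rules:

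> Prolonged hyperglycemia: ketones >1.0 mmol/L with meter BG ≥300 mg/dL, where either meter BG stays ≥300 mg/dL for over 1 hour, or the check followed unexplained CGM >300 mg/dL for 1 hour or >250 mg/dL for 2 hours.

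In 7.4.1 and 9.2, replace the definition with a reference to 9.6. Leave the instructions on changing the Pod or infusion set and contacting the site as they are. Align the adverse event form guidance.

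Simply deleting the hour from 9.6 is tempting but goes too far. It would count a single meter reading with a known cause, which neither current definition covers (last row of the table). The union loses no event reportable under either rule and adds none outside both.

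The cost is one reworded item, two cross-references, matching form guidance, and some additional adverse event forms in both arms. The documents give no basis for saying how many.
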